10.4.2.5. Parkinsonism (UPDRS II and III)

Descriptive summaries of scores on the UPDRS II, the UPDRS III, a composite for the sum of UPDRS II and III scores, and the UPDRS 5-item subscale score will be presented separately for each study visit, disease type, and treatment group.

Statistical significance of between-group differences in change in mean UPDRS II, UPDRS III, UPDRS II and III composite, and the UPDRS 5-item subscale scores from baseline (V4) to EOS (V5/ET) will be tested for the DLB patient subgroup, the PDD patient subgroup, and all patients using univariate ANCOVA models that include treatment arm as a fixed effect, and both the baseline value of the endpoint and status (presence/absence) of background treatment with melatonin/clonazepam (or other benzodiazepines) as covariates. The models for all patients will also include disease type (DLB or PDD) and the treatment arm by disease type interaction as fixed effects.

For each treatment group by each disease type, mean change in UPDRS II and III composite scores from baseline to EOS will be compared to the established threshold for minimal clinically important change of 5 points (Cummings et al, 2014). Further, the proportion of subjects in each treatment arm with an increase in UPDRS II and III composite scores from baseline to EOS of at least 5 points will be calculated and compared using Fisher’s exact tests.

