Statistical Methods	
Sample Size: The sample size was determined based on the primary efficacy endpoint, which tests for statistically significant differences between nelotanserin and placebo treatment arms in the change in frequency per 10 minutes of REM sleep of characteristic RBD behaviors (sum of simple/major and complex RBD events), based on video/audio assessment conducted at a sleep laboratory, from baseline to EOS for the DLB subgroup. Based on results of a power analysis, a sample size of 34 subjects (17 subjects per treatment arm) would provide statistical power ($1 - \beta$) of 0.62 to detect a 0.8 unit treatment arm difference (ie, Cohen's $f = 0.4$) in the change from baseline to EOS in the nightly frequency of RBD behaviors measured by video/audio assessment conducted at a sleep laboratory, assuming a standard deviation of 1 unit, using an analysis of covariance (ANCOVA) model with a single 2-level between-groups fixed effect and 2 covariates and a significance level for type I error (α) of 0.05.
 
Primary Efficacy Analysis: Statistical significance of between-group differences in change in frequency per 10 minutes of REM sleep of characteristic RBD behaviors (sum of simple/major and complex RBD events) for the DLB patient subgroup, based on video/audio assessment conducted at a sleep laboratory from baseline to EOS, will be tested using univariate ANCOVA models that include treatment arm as a fixed effect and both baseline value and status (presence/absence) of background treatment with melatonin/clonazepam (or other benzodiazepines) as covariates.
 
Secondary and Exploratory Efficacy Analysis: For secondary and exploratory efficacy endpoints for which treatment comparisons of change in values will be compared across 2 time points (ie, baseline and EOS), statistical significance of between-group differences in change in mean values from baseline to EOS visits will be tested for the DLB patient subgroup, the PDD patient subgroup, and all patients using univariate ANCOVA models that include treatment arm as a fixed effect and both the baseline value of the endpoint and status (presence/absence) of background

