4. OBJECTIVES AND ENDPOINTS

Objectives	Endpoints
Primary	
To assess the effects of nelotanserin versus placebo on the frequency per 10 minutes of REM sleep of characteristic RBD behaviors (sum of simple/major and complex RBD events) in the DLB patient subgroup based on video/audio assessment conducted at a sleep laboratory	The change in frequency per 10 minutes of REM sleep of characteristic RBD behaviors (sum of simple/major and complex RBD events) from baseline (the whole-night sleep study during placebo run-in period) to end of study (EOS) (the whole-night sleep study at the EOS) in the DLB patient subgroup
Key Secondary	
To assess the effects of nelotanserin versus placebo on extrapyramidal symptoms in the DLB patient subgroup based on UPDRS Part III score	The change in UPDRS Part III score from baseline (V4) to EOS (V5/ET) in the DLB patient subgroup
To assess the effects of nelotanserin versus placebo on the frequency per 10 minutes of REM sleep of characteristic RBD behaviors (sum of simple/minor, simple/major, and complex RBD events) in the DLB patient subgroup based on video/audio assessment conducted at a sleep laboratory	The change in frequency per 10 minutes of REM sleep of characteristic RBD behaviors (sum of simple/minor, simple/major, and complex RBD events) from baseline (the whole-night sleep study during placebo run-in period) to end of study (EOS) (the whole-night sleep study at the EOS) in the DLB patient subgroup
Other Secondary	
To assess the effects of nelotanserin versus placebo on in the DLB patient subgroup based on UPDRS Part II (activities of daily living), UPDRS Parts II+III, UPDRS 5-item scores	The change in UPDRS Part II, II+III and UPDRS 5-item scores from baseline (V4) to EOS (V5/ET) in the DLB patient subgroup
To assess the effects of nelotanserin versus placebo on frequency and severity of RBD behaviors (sum of simple/minor, simple/major, and complex RBD events) in the DLB patient subgroup based on video/audio assessment conducted at a sleep laboratory	The change in the proportion of RBD behaviors rated as severe and the composite score based on both severity and frequency of RBD behaviors (sum of simple/minor, simple/major, and complex RBD events) from baseline (V3) to EOS (V5/ET) in the DLB patient subgroup

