Inclusion and exclusion criteria	X ⁵	X		X					
Medical history/demographics	X								
Concomitant medications review	X	X		X				X ⁴	X
Blood alcohol and urine drug screen	X ⁵								
TSH and vitamin B12 ⁸	X ⁵								
Syphilis serology ⁸	X ⁵								
HBsAg, hepatitis C antibody ⁸	X ⁵								
Beta-glucosidase leukocyte ⁸	X ⁵								
Serum chemistry ^{8,16}	X ⁵			X	X ¹⁶		X	X ⁴	X ⁴
Hematology ⁸	X ⁵			X			X	X ⁴	X ⁴
Urinalysis ⁸	X ⁵			X			X	X ⁴	X ⁴
Bile acids ^{8,15}	X ⁵			X	X ¹⁶		X	X ⁴	X ⁴
PT, INR ⁸	X ⁵			X	X ¹⁶		X	X ⁴	X ⁴
PK sample ⁹				X			X	X ⁴	
Neurological examination	X ⁵			X			X	X ⁴	X ⁴
Physical examination	X ⁵	X		X			X	X ⁴	X ⁴
12-lead ECGs ⁶	X ⁵			X			X	X ⁴	X ⁴
Vital signs ⁷	X ⁵	X		X			X	X ⁴	X ⁴
Review adverse events		X		X	X		X	X ⁴	X
C-SSRS ¹⁴	X ⁵			X			X	X ⁴	X

Study Visit Number:	Screening	Single-Blind Placebo Run-in (Period A)		Double-Blind Treatment (Period B)			Early Termination	Un-scheduled Visit	Follow-up Visit/Phone Contact
		V1 (Screening)	V2 (Run-In) ¹	V3 (Baseline Sleep Labs) ^{1,3}	V4 (Randomization) ^{1,2}	Phone Contact/Lab ^{1,16}			
Visit Type:	Clinic	Clinic	Clinic	Clinic	Phone	Clinic	Clinic		Follow up ¹
Duration:	Up to 28 Days	14 to 30 Days		28 to 40 Days					Clinic/Phone
Study Day: (relative to Randomization unless specified ¹)			14 (+10) after V2	0	14 (-3/+7)	28 (+10)	30 (+10)		14 (-3/+7) after V5 (Clinic)
MMSE	X ^{5,10}			X			X		
MoCA	X ^{5,10}			X			X		
SCOPA - Sleep		X		X			X		
VAS bed partner sleep quality ¹⁸		X		X			X		
CGIC – RBD							X		
UPDRS, Part II and Part III ¹³		X		X			X		
Video-PSG/sleep laboratory ³			X			X		X ⁴	
ActiGraph activity monitor									
Data entry for study diary									
Dispense/collect study diary		X					X		
Review study diary							X		
Dose adjustment instruction							X ¹⁷		
Dispense study drug		X					X		
Return study drug							X		

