10.2. Sample Size Considerations

The sample size was determined based on the primary efficacy endpoints, which test for statistically significant differences between nelotanserin and placebo treatment arms in the change in frequency per 10 minutes of REM sleep of characteristic RBD behaviors (sum of simple/major and complex RBD events), based on video/audio assessment conducted at a sleep laboratory, from baseline to EOS for the DLB subgroup. Based on results of a power analysis, a sample size of 34 subjects would provide statistical power ($1 - \beta$) of 0.62 to detect a 0.8 unit treatment arm difference (ie, Cohen's $f = 0.4$) in the change from baseline to EOS in the nightly frequency of RBD behaviors measured by video/audio assessment conducted at a sleep laboratory, assuming a standard deviation of 1 unit, using an analysis of covariance (ANCOVA) model with a single 2-level between-groups fixed effect and 2 covariates and a significance level for type I error (α) of

0.05.

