10.4.1. Efficacy Analyses

For the primary efficacy endpoint, statistical significance of between-group differences in change in frequency per 10 minutes of REM sleep of RBD behaviors (sum of simple/major and complex RBD events) for the DLB patient subgroup and for the PDD patient subgroup, based on video/audio assessment conducted at a sleep laboratory from baseline to EOS, will be tested using univariate ANCOVA models that include treatment arm as a fixed effect and both baseline value and status (presence/absence) of background treatment with melatonin/clonazepam (or other benzodiazepines) as covariates.

For secondary and exploratory efficacy endpoints for which treatment comparisons of change in values will be compared across 2 time points (ie, baseline and EOS), statistical significance of between-group differences in change in mean values from baseline to EOS visits will be tested for the DLB patient subgroup, the PDD patient subgroup, and all patients using univariate ANCOVA models that include treatment arm as a fixed effect and both the baseline value of the endpoint and status (presence/absence) of background treatment with melatonin/clonazepam (or other benzodiazepines) as covariates. The models for all patients will also include disease type (DLB or PDD) and treatment arm by disease type interaction as fixed effects.

For CGIC-RBD, for which treatment comparisons of difference in values will be compared at EOS (V5/ET) only, statistical significance of between-group differences in mean values will be tested for the DLB patient subgroup, the PDD patient subgroup, and all patients using univariate ANCOVA models that include treatment arm as a fixed effect and baseline status (presence/absence) of background treatment with melatonin/clonazepam (or other benzodiazepines) as a covariate. The model for all patients will also include disease type (DLB or PDD) and the treatment arm by disease type interaction as fixed effects.

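### The DLB key secondary UPDRS Part III ANCOVA is valid but adjusts only for the V4 score, although V2 is also measured before randomised treatment; adding V2 may gain precision without new data.

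*Combined protocol and SAP*

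**What the plan says.** Section 4 defines the first key secondary endpoint as "The change in UPDRS Part III score from baseline (V4) to EOS (V5/ET) in the DLB patient subgroup". Section 10.4.2.5 analyses it by ANCOVA with "treatment arm as a fixed effect, and both the baseline value of the endpoint and status (presence/absence) of background treatment". Section 10.4.1 gives the same covariate list for the other two-time-point endpoints, including SCOPA-Sleep and the bed-partner VAS.

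In Table 2 (section 8.1) the rows "UPDRS, Part II and Part III" and "VAS bed partner sleep quality", and the SCOPA-Sleep row, are marked at V2, V4 and the V5 clinic visit. The extracted table is broken, but the PK row occupies the same V4 and V5 positions, and note 9 confirms those visits. V2 is entry to the single-blind placebo run-in, and note 2 makes V4 the pre-dose baseline. No model in the supplied text uses the V2 scores; they can appear only in the by-visit summaries.

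For CGIC-RBD, section 10.4.1 specifies "treatment arm as a fixed effect and baseline status (presence/absence) of background treatment with melatonin/clonazepam (or other benzodiazepines) as a covariate". No measure of baseline RBD enters that model. Section 10.3.1 requires an evaluable baseline primary assessment for the Full Analysis Set, so every member has a V3 RBD frequency.

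**The concern.** V2 and V4 both precede randomised treatment, so both are legitimate covariates. If V2 still predicts V5 once V4 is known, as it would if a single score carries visit-to-visit measurement noise, leaving it out leaves avoidable variance in the residual.

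The DLB subgroup is small (about 34) and withdrawals in the double-blind period are not replaced (section 6.5.1). No power is stated for UPDRS Part III. Because it measures extrapyramidal symptoms, a wide interval could conceal worsening as well as miss a benefit. The CGIC-RBD model raises the same question: a relevant baseline value exists for everyone analysed and is not used.

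**Working it through.** **Inputs from the documents.** N = 34 in the DLB subgroup, 17 per arm (section 2). Power "of 0.62 to detect a 0.8 unit treatment arm difference", "assuming a standard deviation of 1 unit", with Cohen's f = 0.4 and two covariates (section 10.2). "significance level for type I error (α) of 0.05" (section 2), taken as two-sided because the test is an F test. No correlation between visits, and no SD or effect for UPDRS, SCOPA-Sleep, VAS or CGIC-RBD, is given. All correlations below are therefore assumptions, and an effect of 0.8 residual SD is used only as a scale.

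**Step 1: reproduce the stated figure.** Noncentral F with λ = f²N = 0.16 × 34 = 5.44 and df = (1, 30) gives power 0.617, against 0.62 stated. It agrees. This figure belongs to the primary video-PSG endpoint, which is not measured at V2 and is unaffected by anything here.

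**Step 2: residual variance with and without V2.** Let r24, r25 and r45 be the V2-V4, V2-V5 and V4-V5 correlations.
- V4 only: 1 − r45².
- V4 and V2 as separate covariates: 1 − (r25² + r45² − 2·r24·r25·r45)/(1 − r24²). With all three equal to r, this is 1 − 2r²/(1 + r).

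Formula power rescales the standardised effect by 1/√ratio and uses df = (1, 29).

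| r24, r45 | r25 | V4 only | V4 + V2 | Ratio | Formula power |
|---|---|---|---|---|---|
| 0.5 | 0.5 | 0.750 | 0.667 | 0.889 | 0.667 |
| 0.7 | 0.7 | 0.510 | 0.424 | 0.830 | 0.696 |
| 0.8 | 0.8 | 0.360 | 0.289 | 0.802 | 0.711 |
| 0.8 | 0.75 | 0.360 | 0.326 | 0.907 | 0.658 |
| 0.8 | 0.70 | 0.360 | 0.350 | 0.972 | 0.628 |
| 0.8 | 0.64 | 0.360 | 0.360 | 1.000 | 0.616 |

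In the equal-correlation rows the cut of 11 to 20% is worth 34/0.889 = 38 to 34/0.802 = 42 subjects. The last row is first-order decay (0.8 × 0.8 = 0.64), where V2 adds nothing given V4.

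**Step 3: simulation.** The formula ignores chance imbalance in covariates between small arms, so simulated power is lower throughout. With 17 per arm and the background covariate included, V4 only compared with V4 + V2 gives:
- equal 0.7: about 0.59 to 0.65-0.66;
- equal 0.8: 0.590 to 0.674;
- r25 = 0.75, others 0.80: 0.59 to 0.61-0.62;
- r25 = 0.70: 0.589 to 0.587, no gain;
- r25 = 0.64: 0.589 to 0.574, a loss of 1.5 points, or about 2.

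**Step 4: separate covariates, not the mean.** Replacing V4 by the V2/V4 average does slightly better when correlations are equal. Under first-order decay, however, it inflates residual variance by a factor of 1.178 and formula power drops to 0.548. Separate covariates avoid that.

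**Step 5: PDD subgroup.** About 52 − 34 = 18 subjects, or 9 per arm. With the effect set to give about 0.60 power, adding V2 moves simulated power from 0.606 to 0.569 at r25 = 0.64, nearly 4 points, and from 0.604 to 0.582 at r25 = 0.70.

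**Step 6: CGIC-RBD.** The present model has one covariate: df = (1, 31), formula power 0.618 on the same scale. Adding V3 frequency with correlation ρ to the rating multiplies residual variance by 1 − ρ² and leaves df = (1, 30).
- ρ = 0: 0.617.
- ρ = 0.3 (factor 0.91): 0.658.
- ρ = 0.5 (factor 0.75): 0.741.

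These are formula values. As in Step 3, the real cost at ρ = 0 would be somewhat more than the 0.1 point shown.

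**The case against.** The plan contains no error here. Change from a pre-dose V4 value, with V4 as covariate, is a valid analysis and matches the stated baseline. This stands, and the point is one of efficiency only.

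A reader might infer that precision is certainly being lost. The documents do not support that. V2 is before placebo, V4 is at least two weeks later on placebo, and V5 is about 30 days after V4, so some decay in correlation is plausible. The gain in power is already gone at V2-V5 0.70 with the others at 0.80.

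A reader might also cite the protocol's reference to fluctuation as a core feature of DLB and PDD. Section 3.1.1 speaks of attention, not motor score. For UPDRS the protocol limits visit noise by asking for on-state testing where possible, consistent timing after the dopaminergic dose, and the same assessor where possible (sections 8.3.1 and 8.3.2.7). Nothing shows that the V4 motor score is noisy.

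The case is weaker for the other scales. SCOPA-Sleep asks about the past month, so the V2 and V4 recall windows can overlap, and the VAS is optional without a bed partner. For CGIC-RBD, the rating is itself a judgement of change, so its correlation with baseline frequency could be near zero.

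Finally, section 10.4 defers further detail to a SAP whose text is not in the supplied document. That does not undo covariate lists the protocol already states, though a SAP could add to them.

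**Conclusion.** A modest, optional gain in efficiency for the DLB UPDRS Part III test; the V4-only ANCOVA is neither biased nor invalid. The factual basis is firm: two pre-randomisation scores are collected and one is used. The size is not. At 34 subjects, simulated power on the illustrative scale moves by between about −2 points (first-order decay) and +6 to +8 points (equal correlations 0.7 to 0.8), and the documents do not place the trial within that range. The balance favours adding V2 in the DLB model, but not in the PDD subgroup, where the possible loss is larger. The CGIC-RBD addition follows the same logic and likewise rests on an assumed correlation. The stated 0.62 for the primary endpoint is correct and unchanged.

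**What to change.** Before unblinding, pre-specify:

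1. In the DLB-subgroup UPDRS Part III ANCOVA (section 10.4.2.5 or the SAP), add the V2 score as a separate covariate beside V4, not their mean. Keep V4 as the baseline for the change score. Fill a missing V2 value from a regression on V4 pooled over arms, so that no subject is dropped.
2. In the DLB CGIC-RBD ANCOVA (section 10.4.1 or the SAP), add V3 RBD frequency as a covariate.
3. Treat extension to the other UPDRS scores, SCOPA-Sleep and the VAS as optional. Do not extend the V2 covariate to the PDD subgroup models.

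The cost is one degree of freedom per model and a wording change; no new data are needed. If the change is made in the protocol, section 11.2.1 requires IRB/IEC submission and approval before implementation.

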10.4.2.6. MMSE

Descriptive summaries of scores on the MMSE will be presented separately for each study visit, disease type, and treatment group.

10.4.2.7. MoCA

Descriptive summaries of scores on the MoCA will be presented separately for each study visit, disease type, and treatment group.

10.4.3. Pharmacokinetic/Pharmacodynamic (PK/PD) Analyses

Plasma nelotanserin and M1 metabolite concentrations will be listed and summarized by visit. Exploratory PK/PD analysis will include a scatter plot of plasma nelotanserin and M1 concentrations collected at Visit 5 versus the change in nightly frequency of RBD behaviors from baseline to EOS. Additional analyses (if any) will be specified in the SAP.

10.4.4. Other Analyses

Additional analyses of the data may be conducted as deemed appropriate and will be detailed in the SAP. Further analyses of the data not specified in the SAP may be undertaken as post hoc analyses after completion of the study. Results of all study assessments will be included in an appendix to the study report.

11. RESPONSIBILITIES

11.1. Investigator Responsibilities

11.1.1. Good Clinical Practice

The investigator will ensure that this study is conducted in accordance with the principles of the “Declaration of Helsinki” (as adopted by the World Medical Association 64th General Assembly in Brazil, October 2013), International Conference on Harmonisation (ICH) guidelines, or with the laws and regulations of the country in which the research is conducted, whichever affords the greater protection to the study subject. The investigator will ensure that the basic principles of “Good Clinical Practice,” as outlined in 21 Code of Federal Regulations (CFR) 312, subpart D, “Responsibilities of Sponsors and Investigators,” 21 CFR, part 50, 1998, and 21 CFR, part 56, 1998, are adhered to. These standards are consistent with the requirements of the European Community Directive 2001/20/EC, which shall be adhered to.

Since this is a “covered” clinical trial, the investigator will ensure that 21 CFR, Part 54, 1998, is adhered to; a “covered” clinical trial is any “study of a drug or device in humans submitted in a marketing application or reclassification petition subject to this part that the applicant or FDA relies on to establish that the product is effective (including studies that show equivalence to an effective product) or that make a significant contribution to the demonstration of safety.” This requires that investigators and all sub-investigators must provide documentation of their financial interest or arrangements with the Sponsor, or proprietary interests in the drug being studied.

This documentation must be provided before participation of the investigator and any sub-investigator. The investigator and sub-investigator agree to notify the Sponsor of any change reportable interests during the study and for one year following completion of the study. Study completion is defined as the date that the last subject has completed the protocol defined activities.

This study is also subject to and will be conducted in accordance with 21 CFR, part 320, 1993, “Retention of Bioavailability and Bioequivalence Testing Samples.”

11.1.2. Institutional Review Board/Independent Ethics Committee Approval

This protocol and any accompanying material to be provided to the subject and caregiver (such as advertisements, subject information sheets, or descriptions of the study used to obtain informed consent) will be submitted by the investigator to an IRB or IEC. Approval from the IRB or IEC must be obtained before starting the study and should be documented in a letter to the investigator specifying the protocol number, protocol version, protocol date, documents reviewed, and date on which the committee met and granted the approval.

Any modifications made to the protocol or other documents described in the above paragraph after receipt of IRB or IEC approval must also be submitted to the IRB or IEC for approval before implementation.

11.1.3. Informed Consent

The investigator is responsible for obtaining written informed consent from each individual participating in this study after adequate explanation of the aims, methods, objectives, and

potential hazards of the study and before undertaking any study-related procedures. The investigator must utilize an IRB- or IEC-approved consent form for documenting written informed consent. Each informed consent will be appropriately signed and dated by the subject or the subject's legally authorized representative and the person obtaining consent. Consent from both the caregiver representative and subject should be obtained, if possible.

